7.6.4.3. Laboratory Testing

All laboratory samples (including ADA samples) will be collected after assessments are performed and before a dose of study drug is administered at visits that correspond with a dosing day. At visit 4, study drug may be administered prior to study assessments.

Samples for laboratory testing will be collected at time points according to [Table 1](#) and analyzed by a central laboratory during the study. Detailed instructions for blood sample collection are in the laboratory manual provided to study sites. Specific tests are listed below.

Blood Chemistry

Sodium	Total protein
Potassium	Creatinine
Chloride	Blood urea nitrogen
Bicarbonate	Lactate dehydrogenase (LDH)
Calcium	Phosphorus
Glucose	Uric acid
Albumin	Gamma-glutamyl transpeptidase

Hematology

Hemoglobin	Differential:
Hematocrit	Neutrophils
Red blood cells (RBCs)	Lymphocytes
White blood cells (WBCs)	Monocytes
Platelet count	Basophils
Reticulocyte count	Eosinophils
RBC distribution width	

Urinalysis

Color	Glucose	RBCs
Clarity	Blood	Hyaline and other casts
pH	Bilirubin	Bacteria
Specific gravity	Leukocyte esterase	Epithelial cells
Ketones	Nitrite	Crystals
Protein	WBCs	Yeast

Other Laboratory Tests

Pregnancy testing (serum or urine) will be performed at time points according to [Table 1](#).

Samples for the liver panel (alanine aminotransferase [ALT], aspartate aminotransferase [AST], alkaline phosphatase, and total bilirubin), hepatitis C antibody, hepatitis B surface antigen, hemoglobin A1c (HbA1c), creatine phosphokinase (CPK), thyroid-stimulating hormone (TSH), high-sensitivity C-reactive protein (hs-CRP), and gonadal hormones (for female patients - estradiol, follicle-stimulating hormone [FSH] and luteinizing hormone [LH]; for male patients – testosterone, FSH and LH) will be collected at time points according to [Table 1](#).

Abnormal Laboratory Values and Laboratory Adverse Events

- All laboratory values must be reviewed by the investigator or authorized designee.
- Significantly abnormal tests must be repeated to confirm the nature and degree of the abnormality. When necessary, appropriate ancillary investigations should be initiated. If the abnormality fails to resolve or cannot be explained by events or conditions unrelated to the study medication or its administration, the medical monitor must be consulted.
- The clinical significance of an abnormal test value, within the context of the disease under study, must be determined by the investigator.

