9.5.2.7. Laboratory Data and Vital Signs

The following definitions will be applied to laboratory parameters and vital signs:

- The baseline value is defined as the last available value before first dose of study treatment.
- The PCSA values are defined as abnormal values considered medically important by the sponsor according to predefined criteria/thresholds based on literature review and defined by the sponsor for clinical laboratory tests and vital signs.
- The PCSA criteria will determine which patients had at least 1 PCSA during the TEAE period, taking into account all evaluations performed during the TEAE period,

including unscheduled or repeated evaluations. The number of all such patients will be the numerator for the PCSA percentage.

- Treatment period: the treatment period used for quantitative analysis (laboratory results and vital signs) is defined as the time from first dose of study treatment to the last dose of study treatment + 21 days.

Summary statistics (including mean, median, Q1, Q3, standard error, minimum and maximum) of all laboratory variables and all vital sign parameters (raw data and changes from baseline) will be calculated for each visit, last and worst value assessed during the treatment period, and presented by treatment group. For selected parameters, mean changes from baseline with the corresponding standard error will be plotted over time (at same time points) in each treatment group.

The incidence of PCSAs at any time during the TEAE period (on-treatment PCSAs) will be summarized by treatment group, whatever the baseline level and/or according to the following baseline categories:

- Normal/missing
- Abnormal according to PCSA criteria

For laboratory parameters for which PCSA criteria is not defined, similar table(s) using the normal range could be provided.

Hepatitis C Test

The number and percentage of patients with an observed seroconversion for hepatitis C test will be provided by treatment group.

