The number and percentage of patients with a post-baseline seroconversion for hepatitis C test will be provided by treatment group in post-baseline (including the TEAE and post TEAE periods) as well as in the TEAE period alone. Post-baseline seroconversion is defined for patients with a negative baseline status who had either a “positive RNA” or a “confirmed positive antibody with negative RNA” post-baseline status as defined in the table below. Other situations require case by case evaluation and will be described individually if relevant.

The status as regards hepatitis C virus for a patient will be defined as follows for all evaluations (baseline and post-baseline).

Table 1: Definition of the patient status regarding hepatitis C virus

		Hepatitis C Antibody test result			
		Negative		Positive	
Reflexive test ^a – hepatitis C RNA test	Not available or HCV RNA not detected	HCV RNA detected	HCV RNA not detected ^b	HCV RNA detected	Not available
Hepatitis C status – label	Negative	Positive RNA	Negative ^b	Positive RNA	Positive Ab – no RNA available

^a test performed at the same time or after the antibody test in pre-treatment period (for baseline evaluation), or post-baseline, respectively

^b For post-baseline evaluation, a second antibody test with a different type of assay is to be done at the same date or after the first antibody test. The result of this test will modify the final hepatitis C status of the patient in some cases (see details in the text below the table)

The baseline evaluation will be based on tests performed during the pre-treatment period.

In case of multiple hepatitis C tests available for the post-baseline evaluation, the positive status of the patient will be defined as follows:

- “Positive RNA” status if at least 1 post-baseline positive RNA is detected, regardless of status of the patient at the end of treatment.
- Else “Positive Ab – no RNA available” status if no post-baseline reflexive RNA test is available for at least 1 post-baseline positive antibody test.

If no antibody test is available or with “indeterminate” as result pre-treatment or post-baseline respectively, the RNA test (if available) will be used alone to determine the status of the patient. If no RNA test is available then the hepatitis C status of the patient will be missing.

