The post-baseline status “confirmed positive antibody with negative RNA” will replace “Negative” status as defined above in the case where no RNA was detected post-baseline and the 2 antibody tests surrounding the same visit (from 2 different types of assay) are positive.

For a conservative approach, the post-baseline status “Positive Ab – no RNA available” will not be modified by the availability of a second antibody test from a different assay.

For the description of the positive hepatitis C virus test during the TEAE period, all above rules will apply while replacing post-baseline by TEAE period.

Drug-induced liver injury

The liver function tests, namely AST, ALT, ALP, and total bilirubin, are used to assess possible drug-induced liver toxicity. The proportion of patients with PCSA values or ALT increase as defined as AESI (see Section 4.7.1.2) during TEAE period by baseline status will be displayed by treatment group for each parameter.

An evaluation of drug-induced serious hepatotoxicity (eDISH) with the graph of distribution of peak values of ALT versus peak values of total bilirubin will also be presented using post-baseline values during TEAE period. Note that the ALT and total bilirubin values are presented on a logarithmic scale. The graph will be divided into 4 quadrants with a vertical line corresponding to $3 \times \text{ULN}$ for ALT and a horizontal line corresponding to $2 \times \text{ULN}$ for total bilirubin.

Listing of possible Hy's law cases identified by treatment group (i.e., patients with any elevated $\text{ALT} > 3 \times \text{ULN}$, and associated with an increase in bilirubin $> 2 \times \text{ULN}$, concomitantly or not) with ALT, AST, ALP, total bilirubin, and if available direct and indirect bilirubin will be provided.

The incidence of liver-related TEAEs will be summarized by treatment group. The selection of PTs will be based on SMQ Hepatic disorder (see Section 4.7.1.2).

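### SAP 5.7.2 counts hepatitis C seroconversion only when an RNA result exists, so a patient antibody-positive on two assays but without RNA falls outside the by-arm count

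*SAP*

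**What the plan says.** **Definition.** SAP 5.7.2 reports the number and percentage of patients with post-baseline hepatitis C seroconversion by arm, over the whole post-baseline period and again for the TEAE period alone. It covers baseline-negative patients "who had either a “positive RNA” or a “confirmed positive antibody with negative RNA” post-baseline status as defined in the table below". For everything else the SAP says: "Other situations require case by case evaluation and will be described individually if relevant".

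**Antibody positive, RNA missing.** SAP Table 1 labels this patient *Positive Ab – no RNA available*. With several post-baseline tests, an RNA-positive result ranks first. Next comes the no-RNA "status if no post-baseline reflexive RNA test is available for at least 1 post-baseline positive antibody test".

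**Second assay.** The confirmed-positive status may replace *Negative* only, when post-baseline RNA was not found and two different assays around one visit both gave a positive result. As for the no-RNA status, the SAP states that as a conservative measure it "will not be modified by the availability of a second antibody test from a different assay".

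**Protocol.** Section 7.6.4.3 lists "hepatitis C antibody, hepatitis B surface antigen" among the laboratory tests and names neither RNA nor a second antibody assay. Section 9.5.2.7 plans the number and percentage of "patients with an observed seroconversion for hepatitis C test", with no further definition.

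**The concern.** The same serology is treated differently according to whether an RNA result is on file. Two positive antibody assays count as seroconversion when RNA is detected and also when it is not. RNA therefore does not decide the matter when it is present, yet its absence takes the patient out of the count.

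The label is held fixed in the name of caution, but the only hepatitis C summary that 5.7.2 plans is the seroconversion count, and this label does not enter it. New positives are likely to be few in each arm, so one or two cases moved from the table to a narrative could change what the table appears to show. The narrative route has no stated criteria for relevance.

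**Working it through.** The plan gives no numerical figure to reproduce. The check applies the SAP's status rules to every possible result.

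**Inputs.** SAP Table 1, the text and footnotes below it, and the seroconversion definition above it. Assume a negative baseline status and one post-baseline visit. The first antibody test has 2 possible results, RNA has 3 and the second assay has 3: 2 × 3 × 3 = 18 combinations.

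| First antibody | RNA | Second assay not done | Second assay negative | Second assay positive |
|---|---|---|---|---|
| Positive | Detected | counted | counted | counted |
| Positive | Not detected | not counted | not counted | counted |
| Positive | Not available | not counted | not counted | **not counted** |
| Negative | Detected | counted | counted | counted |
| Negative | Not detected | not counted | not counted | not counted |
| Negative | Not available | not counted | not counted | not counted |

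**Result.** 3 + 1 + 3 = 7 of the 18 combinations are counted: the 6 with RNA detected, and the 1 with two positive assays and RNA not detected. None of the 6 combinations without RNA is counted. The cell in bold is the inconsistent one.

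**Direction of the fixed-label rule** (third row of the table). If the second assay is negative, the patient keeps a positive label instead of reverting to *Negative*, which is cautious about the label. If it is positive, the label cannot move to a status that counts, so for the count the rule works downwards.

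**Size.** Let m be the share of two-assay positives without RNA. The formal count captures 1 − m of them. The documents give no m, so these values are assumptions:

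- m = 0%: 100% captured
- m = 5%: 95%
- m = 10%: 90%
- m = 25%: 75%
- m = 50%: 50%

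**More than one post-baseline sample.** Suppose an early sample is confirmed positive with RNA not detected, and a later sample is antibody positive with no RNA. The second rule in the status order is met, because at least one positive antibody test lacks RNA. The confirmed status may replace only *Negative*, so read literally it does not apply, and a patient already confirmed leaves the count. In the reverse order the problem does not arise: footnote a to SAP Table 1 accepts an RNA test done at the same time as the antibody test or after it, so the later RNA result can serve the earlier sample. Only one post-baseline sample is scheduled, at week 96 (Protocol Table 1; SAP 4.7.2). A second one can arise when a patient stops study drug early, because Protocol 7.3.1 asks for end-of-study assessments at that point and then a return to the schedule.

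**The case against.** Several points on the other side are sound.

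- **The patients are not discarded.** The SAP requires case-by-case evaluation of other situations. For a handful of cases individual description is reasonable. It is still not the n (%) by arm, and only relevance, undefined, decides whether a case is described.
- **RNA is meant to follow the antibody result.** SAP Table 1 calls it reflexive, and Protocol 7.6.4.3 requires significantly abnormal tests to be repeated. Footnote b attaches the second assay to the cell where RNA is already known to be not detected. Two positive assays without RNA would depart from that sequence. This stands as a reason to expect few cases. The SAP nevertheless foresees the case, since it writes a rule for it.
- **The conservative label is fair in one direction,** as shown above.

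A reader might infer three stronger things that the documents do not support. One is that RNA will usually be missing because the protocol lists only the antibody test. A reflex test need not appear in a list of scheduled tests, and the laboratory manual is not among the documents. The second is that all confirmed seroconversions could be lost if only the listed tests are run. That list has no second assay either, so no patient would be confirmed and the share would be undefined. The third is that the SAP contradicts the protocol. The protocol leaves observed seroconversion undefined, and the SAP may give it a working definition.

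**Conclusion.** The point holds as an inconsistency in a prespecified rule. A baseline-negative patient with two positive assays is in the by-arm count with either RNA result and outside it with none. The single-visit result follows from the SAP text. The displacement across visits depends on a literal reading of the status order, on a second post-baseline sample, and on one particular order of results.

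The shortfall equals the unknown share without RNA and may be zero. The table is descriptive, with no inferential testing, and has no bearing on the cognitive endpoint. This is a minor correction, worth making because it is cheap and because few events are likely.

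**What to change.** In SAP 5.7.2:

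1. Count as seroconversion a baseline-negative patient whose post-baseline antibody is confirmed positive by the second assay and who has no RNA result.
2. State that a confirmed positive antibody at any post-baseline visit is not displaced by a no-RNA result at another visit.
3. Add an n (%) row by arm, headed possible seroconversion, for baseline-negative patients left as *Positive Ab – no RNA available* without a positive second assay.
4. Keep the sentence about the conservative approach, but limit it to a negative second assay.

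Apply the same changes to the TEAE-period version of the count. The cost is a few lines of SAP text and one table row. No procedure, sample or other analysis changes. The downside is that the seroconversion figure may rise slightly.

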5.7.3. Analysis of Vital Sign Variables

The vital sign actual values and change from baseline values obtained while sitting will be descriptively summarized at baseline and each post-baseline visit (collected up to the day of last dose of study treatment +21 days) by at least patient number, mean, median, Q1, Q3, SD, minimum and maximum for each treatment group. Additionally, vital sign measures for last on-treatment value and worst on-treatment value will be summarized in a similar manner. Vital sign mean changes from baseline, with the corresponding SE, can be plotted at each visit by treatment group, in the case results warrant further investigation.

Individual patient vital sign measurements (regardless of sitting position) will be additionally evaluated by PCSA criteria, specifically identifying patients with at least one post-baseline measurement that meets the PCSA criteria within the TEAE period. Patients meeting the PCSA criteria at least once will be summarized by patient count (and percent) and treatment group. Patient listings of vital sign measurements that meet PCSA criteria will be provided for the report appendix.

5.8. Analysis of Other Variables

The summary of other variables will be presented by treatment groups (Praluent, placebo) on the safety population. No formal inferential testing will be performed for either period. Summaries will be descriptive in nature.

All measurements, scheduled or unscheduled, fasting or not fasting, will be assigned to analysis windows in order to provide an assessment for week 8 to week 96 time points.

Hs-CRP and HbA1c parameters (Section 4.8) will be summarized by treatment group for the number of patients with data, mean, SD, median, minimum, and maximum (for hs-CRP, Q1 and Q3 will be also provided) by analysis visit during the treatment period. For HbA1c, summaries will also be provided according to diabetes mellitus status at baseline. The time profile will be plotted by treatment group for HbA1c showing the means and the corresponding SEs, while medians (with Q1-Q3) will be plotted for hs-CRP. Applying the PCSA criteria to these variables at any time during the TEAE period, the number of patients (and percentages) meeting the criteria will be summarized by treatment group.

The gonadal hormone parameters (Section 4.8) will be summarized by treatment group for the number of patients with data, mean, SD, median, minimum, and maximum by analysis visit during the treatment period. For FSH and LH, the summaries will be performed for all patients, female patients, and male patients. Estradiol will be summarized for female patients only, and testosterone will be summarized for male patients only. Summary tables will also be provided for gonadal hormone parameters based on measurements outside the central laboratory normal ranges, if applicable.

In order to minimize confounding factors with menopause or exogenous estrogens, the summaries of estradiol, FSH, and LH for female patients will be repeated by excluding patients who were receiving hormone replacement therapy, were ≥ 50 years, or had FSH levels ≥ 25 IU/L at baseline.

For male patients, the summaries of testosterone, FSH, and LH will be repeated by excluding patients who were receiving testosterone supplementation or had LH levels ≥ 15 IU/L at baseline.

Binary endpoints defined in Section 4.8 will be described through patient counts and percentages. Kaplan-Meier curves will be provided for the variables assessing time to first occurrence of an event (i.e., calculated LDL-C related outcome). Patients not meeting the event will be censored at the end of the treatment period. For the analysis of the time to the first of the two consecutive LDL-C events, patients without post-baseline LDL-C result or with only one post-baseline LDL-C result will not be included in the analysis.

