4.2.1. Inclusion Criteria

A patient must meet the following criteria to be eligible for inclusion in the study:

1. Men and women \geq age 40 and \leq age 85
2. Patients with heFH (see [Appendix 1](#) and [Appendix 2](#) for diagnosis criteria) or non-FH patients at high or very high cardiovascular risk

High and very high cardiovascular risk patients include patients with coronary heart disease (CHD), non-CHD CVD, and other risk factors. Definitions for CHD, non-CHD CVD, and other risk factors:

- a. A documented history of CHD (includes 1 or more of the following):
 - i. Acute myocardial infarction
 - ii. Silent myocardial infarction
 - iii. Unstable angina
 - iv. Coronary revascularization procedure (eg, percutaneous coronary intervention or coronary artery bypass graft surgery)
 - v. Clinically significant CHD diagnosed by invasive or non-invasive testing (eg, coronary angiography, stress test using treadmill, stress echocardiography, coronary calcium scan, or nuclear imaging).
- b. Non-CHD CVD (includes 1 or more of the following criteria):
 - vi. Documented previous ischemic stroke with a focal ischemic neurological deficit that persisted more than 24 hours, considered as being of atherothrombotic origin. Computed tomography (CT) or magnetic resonance

imaging (MRI) must have been performed to rule out hemorrhage and non-ischemic neurological disease.

- vii. Peripheral arterial disease
- viii. Abdominal aortic aneurysm
- ix. Atherosclerotic renal artery stenosis
- x. Carotid artery disease (transient ischemic attacks or >50% obstruction of a carotid artery)

c. Other risk factors

- xi. Documented moderate chronic kidney disease as defined by $30 \leq$ Estimated Glomerular Filtration Rate (eGFR) <60 mL/min/1.73 m² for 3 months or more, including the screening visit
- xii. Type 1 or type 2 diabetes mellitus
- xiii. A calculated 10-year fatal CVD risk SCORE $\geq 5\%$ (ESC/EAS Guidelines for the management of dyslipidemias, [Perk 2012](#))

* For CVD risk categories, see [Appendix 5](#).

3. Patients with history of CHD not having adequate control of their hypercholesterolemia with LDL-C ≥ 70 mg/dL, or all other patients with LDL-C ≥ 100 mg/dL

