4.8. Other Variables

Other assessment endpoints are listed and defined below. Protocol schedule visits will be assigned to the Analysis Windows (See Appendix 10.2).

- The percent change in hs-CRP from baseline to protocol specified visits. Hs-CRP values greater or equal to 10 mg/L will be excluded from analyses in a second approach, since these are suggestive of concurrent infection(1). PCSA (potentially clinically significant abnormalities) criteria for hs-CRP are listed in Appendix 10.3.
- The absolute change in HbA1c (%) from baseline to protocol specified visits. PCSA criteria for HbA1c are listed in Appendix 10.3.
- The proportion of patients with two consecutive results, separated by at least 21 days, of calculated LDL-C <25 mg/dL (<0.65 mmol/L) (and again for calculated LDL-C <15 mg/dL [< 0.39 mmol/L]) during the treatment period.
- The proportion of patients with at least one result of calculated LDL-C <25 mg/dL (<0.65 mmol/L) (and again for calculated LDL-C <15 mg/dL [< 0.39 mmol/L]) during the treatment period.
- For the patients with two consecutive results as described above, the time to the first calculated LDL-C <25 mg/dL (<0.65 mmol/L) (and again for calculated LDL-C <15 mg/dL [< 0.39 mmol/L]) during the treatment period.

- Gonadal hormone levels (for female patients - estradiol, follicle-stimulating hormone (FSH) and luteinizing hormone (LH); for male patients - testosterone, FSH and LH)

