5.7. Analysis of Safety Data

The summary of safety results will be presented by treatment groups (Praluent, placebo) on the safety population (Section 3.1). No formal inferential testing will be performed.

Summaries will be descriptive in nature. All summaries of safety results described below will be presented for each period respectively, unless otherwise noted.

General common rules

All safety analyses will be performed, unless otherwise specified, using the following common rules:

- Safety data in patients who do not belong to the safety population (i.e., exposed but not randomized) will be listed separately.
- The baseline value is defined as the last available value obtained up to the date and time of the first study treatment, except otherwise specified.
- PCSA values are defined as abnormal values considered medically important by the Sponsor according to predefined criteria/thresholds based on literature review and defined by the Sponsor for clinical laboratory tests and vital signs (PCSA version dated January 2009 [Appendix 10.3]). Considering that the threshold defined in the PCSA list for monocytes and basophils can be below the ULN, the following PCSA criterion will be used for the PCSA analysis of monocytes and basophils:
 - PCSA criterion for monocytes: >0.7 Giga/L or $>\text{ULN}$ (if $\text{ULN} \geq 0.7$ Giga/L).
 - PCSA criterion for basophils: >0.1 Giga/L or $>\text{ULN}$ (if $\text{ULN} \geq 0.1$ Giga/L).
- PCSA criteria will determine which patients had at least 1 PCSA during the TEAE period, taking into account all evaluations including nonscheduled or repeated evaluations.
- The treatment-emergent PCSA denominator by treatment group for a given parameter will be based on the number of patients assessed for that given parameter at least once during the TEAE period.
- All measurements, scheduled or unscheduled, fasting or not fasting, will be assigned to analysis windows defined in Appendix 10.2, Table 2 in order to provide an assessment for week 8 to week 96 time points.
- For quantitative safety parameters including central laboratory measurements and vital sign scores, descriptive statistics will be used to summarize results and change from baseline values by visit, the last on-treatment value and the worst on-treatment value. The last on-treatment value is defined as the last post-baseline value collected during the respective treatment period (as defined in

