5.7.2. Analysis of Clinical Laboratory Variables

Clinical laboratory parameter actual values (quantitative) and change from baseline values will be descriptively summarized at baseline and each post-baseline visit (collected up to the

day of last dose of study treatment +21 days) by at least patient number, mean, median, Q1, Q3, SD, minimum and maximum for each treatment group. Additionally, laboratory parameter measures for last on-treatment values and worst on-treatment values will be summarized in a similar manner. Clinical laboratory parameters mean changes from baseline, with the corresponding SE, can be plotted at each visit by treatment group, in the case results warrant further investigation. These parameters will be presented by the biological functions defined in Section 4.7.2. For glucose, only fasting samples will be included in the summaries.

Individual patient laboratory parameter measurements will be additionally evaluated by PCSA criteria, specifically identifying patients with at least one post-baseline measurement that meets the PCSA criteria within the TEAE period. The following additional project specific PCSA criteria will also be evaluated during the TEAE period:

- Patients with a hemoglobin decrease from baseline ≥ 15 g/L.
- Patients meeting the ALT increase defined in Section 4.7.1.2.

Glucose (quantitative summary and PCSA) will also be analyzed, overall and according to the diabetic status at baseline.

Patients meeting the PCSA criteria at least once will be summarized by patient count (and percent) for a post-baseline PCSA measurement while accounting for the baseline PCSA status (PCSA normal/missing; PCSA abnormal), for each treatment group. For the appendix, this laboratory parameter PCSA table will be reproduced with patients meeting the PCSA criteria at least once during the TEAE period regardless of baseline PCSA status. These laboratory parameters will be presented by the biological functions defined in Section 4.7.2. Patient listings of laboratory measurements that meet PCSA criteria will be provided for the report appendix. For those laboratory parameters that don't have an associated PCSA criteria, similar summary tables can be provided based on measurements outside the central laboratory normal ranges, if applicable.

Hepatitis C antibody

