eGFR (mL/min/1.73m ²) (Estimate of GFR based on an MDRD equation)	$\geq 15 - < 30$ (severe decrease in GFR) $\geq 30 - < 60$ (moderate decrease in GFR) $\geq 60 - < 90$ (mild decrease in GFR) ≥ 90 (normal GFR)	Use is optional. FDA draft Guidance 2010 Pharmacokinetics in patients with impaired renal function-study design, data analysis, and impact on dosing and labeling
Uric Acid		Harrison- Principles of Internal Medicine 17 th Ed., 2008.
Hyperuricemia	$> 408 \text{ } \mu\text{mol/L}$	
Hypouricemia	$< 120 \text{ } \mu\text{mol/L}$	
Blood Urea Nitrogen	$\geq 17 \text{ mmol/L}$	
Chloride	$< 80 \text{ mmol/L}$ $> 115 \text{ mmol/L}$	
Sodium	$\leq 129 \text{ mmol/L}$ $\geq 160 \text{ mmol/L}$	
Potassium	$< 3 \text{ mmol/L}$ $\geq 5.5 \text{ mmol/L}$	FDA Feb 2005.
Lipasemia	$\geq 3 \text{ ULN}$	
Amylasemia	$\geq 3 \text{ ULN}$	
Glucose		
Hypoglycaemia	$\leq 3.9 \text{ mmol/L}$ and $< \text{LLN}$	ADA May 2005.
Hyperglycaemia	$\geq 11.1 \text{ mmol/L}$ (unfasted); $\geq 7 \text{ mmol/L}$ (fasted)	ADA Jan 2008.

Parameter	PCSA	Comments
HbA1c	>8%	
Albumin	≤25 g/L	
CRP	>2 ULN or >10 mg/L (if ULN not provided)	FDA Sept 2005.
Hematology		
WBC	<3.0 Giga/L (Non-Black); Increase in WBC: not relevant. <2.0 Giga/L (Black) ≥16.0 Giga/L	To be interpreted only if no differential count available.
Lymphocytes	>4.0 Giga/L	
Neutrophils	<1.5 Giga/L (Non-Black); <1.0 Giga/L (Black)	International Consensus meeting on drug-induced blood cytopenias, 1991. FDA criteria.
Monocytes	>0.7 Giga/L	
Basophils	>0.1 Giga/L	
Eosinophils	>0.5 Giga/L or >ULN (if ULN ≥ 0.5 Giga/L)	Harrison- Principles of internal Medicine 17 th Ed., 2008.
Hemoglobin	≤115 g/L (Male); ≤95 g/L (Female) ≥185 g/L (Male); ≥165 g/L (Female)	Criteria based upon decrease from baseline are more relevant than based on absolute value. Other categories for decrease from baseline can be used (≥30 g/L, ≥40 g/L, ≥50 g/L).
Decrease from Baseline ≥20 g/L		
Hematocrit	≤0.37 v/v (Male) ; ≤0.32 v/v (Female) ≥0.55 v/v (Male) ; ≥0.5 v/v (Female)	
RBC	≥6 Tera/L	Unless specifically required for particular drug development, the analysis is redundant with that of Hb. Otherwise, consider FDA criteria.
Platelets	<100 Giga/L ≥700 Giga/L	International Consensus meeting on drug-induced blood cytopenias, 1991.

Parameter	PCSA	Comments
Urinalysis		
pH	≤ 4.6 ≥ 8	
Vital signs		
HR	≤ 50 bpm and decrease from baseline ≥ 20 bpm ≥ 120 bpm and increase from baseline ≥ 20 bpm	To be applied for all positions (including missing) except STANDING.

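### SAP 5.8 counts HbA1c and hs-CRP abnormalities without the baseline split that SAP 5.7.2 gives the other laboratory tests, so pre-existing and new cases are mixed

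*SAP*

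**What the plan says.** SAP 4.8 places HbA1c and hs-CRP among the other variables and sends the reader to the appendix for thresholds, for example "PCSA criteria for HbA1c are listed in Appendix 10.3". SAP Appendix 10.3 sets HbA1c at >8% and CRP at ">2 ULN or >10 mg/L (if ULN not provided"). Neither criterion has a change-from-baseline condition.

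The counting rule is in SAP 5.8: "Applying the PCSA criteria to these variables at any time during the TEAE period, the number of patients (and percentages) meeting the criteria" are to be shown by treatment group. No baseline category is mentioned. SAP 5.8 gives no denominator of its own. The general rule in SAP 5.7 is: "The treatment-emergent PCSA denominator by treatment group for a given parameter will be based on the number of patients assessed for that given parameter". A single assessment in the TEAE period is enough, so patients abnormal at baseline stay in.

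For the routine laboratory tests, SAP 5.7.2 presents patients who meet a PCSA criterion "while accounting for the baseline PCSA status (PCSA normal/missing; PCSA abnormal), for each treatment group", and moves the version that disregards baseline to the appendix. Its scope is tied to a list: "These laboratory parameters will be presented by the biological functions defined in Section 4.7.2". HbA1c and hs-CRP are not on that list.

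Protocol 9.5.2.7 allows either presentation. Laboratory PCSAs are to be "summarized by treatment group, whatever the baseline level and/or according to the following baseline categories", namely normal/missing and abnormal.

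**The concern.** A fixed threshold with no reference to the pre-dose value cannot tell a patient who crossed it on treatment from one who was already over it. That matters for HbA1c because Protocol 4.2.1 lists "Type 1 or type 2 diabetes mellitus" among the qualifying risk factors, and none of the exclusion criteria in Protocol 4.2.2 caps HbA1c. Some patients can be expected to start above 8%.

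Randomization should spread these patients evenly, so they add about the same number of cases to each arm. Equal additions pull the ratio of the two percentages towards 1. In a safety table the cost is that a real difference in new abnormalities is harder to see. The planned baseline table would not let a reader correct for this, because the HbA1c categories in SAP 4.1 stop at 6.5% or more and do not show the share above 8%.

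**Working it through.** **No figure to reproduce.** The documents state no PCSA rate, no share of patients with diabetes and no HbA1c or hs-CRP distribution. The check is a comparison of the text, followed by an illustration.

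**Text comparison**

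- Routine laboratory tests (SAP 5.7.2): split by baseline PCSA status, with the unsplit version in the appendix.
- Glucose (SAP 5.7.2): the same split, and also analysed by diabetic status at baseline.
- Vital signs (SAP 5.7.3): no split, but the heart rate, blood pressure and weight criteria in Appendix 10.3 include a change from baseline.
- HbA1c and hs-CRP (SAP 5.8): no split and no change condition.
- SAP 6.4 says where a patient with a missing baseline is grouped. It does not order a split for any given variable.
- The second hs-CRP approach in SAP 4.8 drops values of 10 mg/L or more. It does not separate patients by baseline status.

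HbA1c and hs-CRP are thus the two laboratory variables with PCSA criteria for which the SAP protects the count from pre-existing abnormality neither by a split nor by a change condition.

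**Illustration**

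Inputs, all assumed:

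- b, the share above threshold at baseline: 2%, 5%, 10%, 15%.
- q, the chance that such a patient is above threshold again in the TEAE period, equal in both arms: 50%, 90%.
- p0 and p1, the new-onset risk on placebo and Praluent among the rest: 3% and 5%.

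Formulas:

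- Placebo percentage = b·q + (1−b)·p0
- Praluent percentage = b·q + (1−b)·p1
- Difference = (1−b)·(p1−p0)
- Pre-existing share of the Praluent count = b·q / Praluent percentage

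With the baseline-normal patients alone, the ratio is 5/3 = 1.67 and the difference 2.0 points at every b. Pooled as in SAP 5.8:

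| b | q | Placebo % | Praluent % | Ratio | Difference (points) | Pre-existing share, Praluent |
|---|---|---|---|---|---|---|
| 2% | 50% | 3.94 | 5.90 | 1.50 | 1.96 | 17% |
| 2% | 90% | 4.74 | 6.70 | 1.41 | 1.96 | 27% |
| 5% | 50% | 5.35 | 7.25 | 1.36 | 1.90 | 34% |
| 5% | 90% | 7.35 | 9.25 | 1.26 | 1.90 | 49% |
| 10% | 50% | 7.70 | 9.50 | 1.23 | 1.80 | 53% |
| 10% | 90% | 11.70 | 13.50 | 1.15 | 1.80 | 67% |
| 15% | 50% | 10.05 | 11.75 | 1.17 | 1.70 | 64% |
| 15% | 90% | 16.05 | 17.75 | 1.11 | 1.70 | 76% |

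One line worked through, b = 5% and q = 90%: placebo 0.045 + 0.95 × 0.03 = 7.35%; Praluent 0.045 + 0.95 × 0.05 = 9.25%; ratio 1.26. With the planned 1085 patients per arm that is about 80 versus 100 patients, of whom 1085 × 0.045, about 49, are pre-existing in each arm.

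With new-onset risks of 5% and 8% instead (ratio 1.60), the pooled ratio runs from 1.50 (b = 2%, q = 50%) to 1.14 (b = 15%, q = 90%).

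**The case against.** The best defence is that much of this ground is covered elsewhere. Glucose PCSAs are split by baseline status and by diabetic status (SAP 5.7.2). Adverse events in the diabetes grouping are analysed in patients with and without diabetes at baseline (SAP 5.7.1). Change in HbA1c from baseline is a defined variable (SAP 4.8). SAP 5.8 itself plans HbA1c summaries by diabetes status. This stands as partial cover. But the sentence on diabetes status comes before the PCSA sentence and may not reach it. If it does, the non-diabetic group would come close to showing new crossings, while the diabetic group would still mix old and new.

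It is also fair to say that Protocol 9.5.2.7 provides for baseline categories and that SAP 1.2.3 declares no departure from the protocol. The gap looks more like an incomplete carry-over into SAP 5.8 than a decision to disregard baseline. Still, the protocol wording permits the split without requiring it.

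Third, the table reports counts and percentages with no formal test, and on the difference scale little is lost: 1.9 points against 2.0 when 5% are abnormal at baseline. That too stands. The loss is mainly in the ratio.

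A reader might infer that most of the counted patients had pre-existing disease. The documents do not support that: in the illustration the share runs from 17% to 76%, depending wholly on assumed inputs. For hs-CRP it is less certain still. The operative threshold is twice the ULN, with 10 mg/L only as a fallback, and the ULN is not given.

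**Conclusion.** The point holds, and it is minor. As written, SAP 5.8 mixes patients already above the HbA1c or hs-CRP threshold with those who cross it on treatment, and nothing else in the plan requires them to be separated in this count. Under the assumed inputs, a new-onset ratio of 1.67 would show as about 1.50 to 1.11, and the risk difference would shrink only by the baseline-abnormal share. The result assumes that pre-existing cases recur at the same rate in both arms.

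Two stronger readings should be set aside. One is that the table would favour Praluent or placebo: pre-existing cases balance in expectation, so the effect is attenuation, although chance imbalance could move the counts either way. The other is that the assessment of new-onset diabetes is compromised: SAP 4.7.1.2 defines it only in patients without diabetes at baseline, with its own HbA1c and fasting glucose rules, and this table does not feed it. The primary analysis is unaffected.

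**What to change.** In SAP 5.8:

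- Tabulate the HbA1c and hs-CRP PCSAs by baseline PCSA status (normal/missing; abnormal), showing both rows as SAP 5.7.2 does. Neither row need be named the main one; the abnormal row keeps poorly controlled diabetic patients in view.
- Keep the count that disregards baseline status in the appendix.
- State that the planned HbA1c summary by baseline diabetes status also applies to the PCSA count.

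The cost is a sentence or two of SAP text and reuse of an existing table layout. No new data are needed: the protocol's schedule of events collects HbA1c at screening and hs-CRP on day 1, and baseline is the last value before the first dose. The change is consistent with Protocol 9.5.2.7.
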